5.3.1 Dose titration

During the first 20 weeks the dose will be titrated every fourth week starting from week 4. The last dose adjustment will be done at week 20. This allows five opportunities for dose adjustment (weeks 4, 8, 12, 16 and 20). Dose titration is based on insulin-like growth factor-I standard deviation score (IGF-I SDS) values used for calculation of the next dose. The dose adjustment calculations will provide the new doses for the subjects in the eCRF. IGF-I, insulin-like growth factor binding protein – 3 (IGFBP-3) and IGF-I SDS results will not be made available to the investigator during the trial.

The dose administered to the subject must be entered in the IWRS.

Subjects will come to the clinic 3 weeks and 3 days after the previous dose adjustment visit for an IGF-I, IGFBP-3 and PK blood sample draw. Handling deviations from this schedule is described in section [5.3.5](#). The dose adjustments are performed at weeks 4, 8, 12, 16 and 20, i.e. four days after the IGF-I titration samples have been collected. Dose adjustments will be provided over the phone, except for the last dose adjustment (week 20) which will happen at site. After last dose adjustment visit (week 20), the individual dose level is fixed.

Besides the IGF-I based dose adjustment during the titration period, dose reduction can be considered during the entire trial period (including the titration period) at the investigator's discretion for safety concerns. If adverse events with a probable relationship to the trial drug are persistent but continuation in the trial is acceptable, as judged by the investigator and subject, dose reduction in steps of 25% can be considered. If, after consecutive dose reduction steps, AEs still persist, the subject's treatment may be discontinued or the subject may withdraw as described in section [6.4](#) and [6.5](#).

If a subject reports symptoms of GH related AEs at a dose adjustment visit, the dose titration in the eCRF should be performed prior to potentially reducing the dose by 25% (performing the dose reduction in the eCRF), as the IGF-I based titration might reduce the dose.

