8.5 Laboratory assessments

The laboratory equipment may provide analyses not requested in the protocol but produced automatically in connection with the requested analyses according to specifications in the laboratory standard operating procedures. Such data will not be transferred to the trial database, but abnormal values will be reported to the investigator. The investigator must review all laboratory results for concomitant illnesses and AEs and report these according to section [8.2.2](#) and section [12](#).

Antibody samples will be stored as described in section [24.2](#). All other laboratory samples will be destroyed no later than at finalisation of the clinical trial report.

All lab reports must be dated and signed by the investigator to document data review.

Surveillance of laboratory safety data (with the exception of PK, biomarkers and anti-drug antibody data) will be performed by a medical specialist at least every 2 months based on safety surveillance reports. If a finding is identified, the medical specialist will immediately inform the chairman of the safety committee.

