8.5.2 Laboratory assessments for safety

Biomarkers (IGF-I and IGFBP-3)

When sampling for IGF-I and IGFBP-3, subjects must be fasting 8 hours before sample collection, with only water allowed. If a subject comes non-fasting to visits during the titration periods, the sampling will be re-scheduled according to section [5.3.5](#).

IGF-I and IGFBP-3 samples will be collected at screening and every second visit during the titration period and throughout the fixed-dose period (see section [2](#)). All samples must be drawn prior to trial drug administration if this is planned on a sampling day. Based on the results, IGF-I SDS values will be calculated by the central lab, transferred to the eCRF and used for dose adjustment during the titration period.

The central laboratory will be responsible for providing age and sex appropriate normal reference ranges of IGF-I and IGFBP-3 and for calculation of IGF-I SDS according to below equation:

$$IGF - I \text{ SDS} = \frac{\left(\left(\frac{IGF - I \text{ value}}{Median} \right)^{Skewness} \right) - 1}{Skewness \times Standard \text{ Deviation}}$$

Median, Skewness and Standard Deviation are based on reference data.

IGF-I SDS values will be used for dose titration of somapacitan and Norditropin[®] FlexPro[®]. Details of the dose titration are described in section [5.3.1](#).

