12.1 Definitions

12.1.1 Adverse event

An adverse event (AE) is, according to GCP definition, any untoward medical occurrence in a subject administered a medicinal product, and which does not necessarily have a causal relationship with this treatment.

An AE can therefore be any unfavourable and unintended sign (including an abnormal laboratory finding), symptom or disease temporally associated with the use of a product, whether or not considered related to the product.

An AE includes:

- A clinically significant worsening of a concomitant illness.
- A clinical laboratory adverse event (CLAE): a clinical laboratory abnormality which is clinically significant, i.e. an abnormality that suggests a disease and/or organ toxicity and is of a severity that requires active management. Active management includes active treatment or further investigations, for example change of medicine dose or more frequent follow-up due to the abnormality.

The following should **not** be reported as AEs:

- Pre-existing conditions, including those found as a result of screening or other trial procedures performed before exposure to trial product (pre-existing conditions should be reported as medical history or concomitant illness).
- Pre-planned procedures unless the condition for which the procedure was planned has worsened from the first trial related activity after the subject has signed the informed consent.

The following three definitions are used when assessing an AE:

- **Severity**
 - **Mild** – no or transient symptoms, no interference with the subject's daily activities.
 - **Moderate** – marked symptoms, moderate interference with the subject's daily activities.
 - **Severe** – considerable interference with the subject's daily activities; unacceptable.
- **Causality**

Relationship between an AE and the relevant trial product(s):

 - **Probable** - Good reason and sufficient documentation to assume a causal relationship.
 - **Possible** - A causal relationship is conceivable and cannot be dismissed.
 - **Unlikely** - The event is most likely related to aetiology other than the trial product.

- **Final outcome**

- **Recovered/resolved** - The subject has fully recovered, or by medical or surgical treatment the condition has returned to the level observed at the first trial-related activity after the subject signed the informed consent.

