12.2 Reporting of adverse events

All events meeting the definition of an AE must be collected and reported. This includes events from the first trial-related activity after the subject has signed the informed consent until the end of the post-treatment follow-up period (week 53). The events must be recorded in the applicable eCRF forms in a timely manner, see timelines below and [Figure 12-1](#).

During each contact with the trial site staff, the subject must be asked about AEs and technical complaints, for example by asking: “Have you experienced any problems since the last contact?”

All AEs, either observed by the investigator or the subject, must be reported by the investigator and evaluated.

All AEs must be recorded by the investigator on an AE form. The investigator should report the diagnosis, if available. If no diagnosis is available, the investigator should record each sign and symptom as individual AEs using separate AE forms.

For SAEs, a safety information form must be completed in addition to the AE form. If several symptoms or diagnoses occur as part of the same clinical picture, one safety information form can be used to describe all the SAEs.

For all non-serious AEs, the applicable forms should be signed when the event is resolved or at the end of the trial at the latest.

Timelines for initial reporting of AEs:

The investigator must complete the following forms in the eCRF within the specified timelines:

[figure not shown]
- **SAEs:** The AE form **within 24 hours** and the safety information form **within 5 calendar days** of the investigator's first knowledge of the SAE.

Both forms must be signed within 7 calendar days from the date the information was entered in the eCRF.

For SAEs requiring reporting on a specific event form (medication error form and injection site reaction form): In addition to the above the specific event form within **14 calendar days** from the investigator's first knowledge of the AE.

If the eCRF is unavailable, the concerned AE information must be reported on a paper AE form and sent to Novo Nordisk by fax, e-mail or courier within the same timelines as stated above. When the eCRF becomes available again, the investigator must enter the information on the form into the eCRF.

Contact details (fax, telephone, e-mail and address) are provided in the investigator trial master file.

Timelines are for the completion of forms from the time of investigator's awareness.

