- Screen failure reason
- AEs and SAEs

Monitors will review the subject's medical records and other source data (e.g. the diaries and PROs) to ensure consistency and/or identify omissions compared to the eCRF. If discrepancies are found, the investigator must be questioned about these.

A follow-up letter (paper or electronic) will be sent to the investigator following each monitoring visit. This should address any action to be taken.

15 Data management

Data management is the responsibility of Novo Nordisk.

Appropriate measures, including encryption of data files containing person identifiable data, will be used to ensure confidentiality of subject data, when they are transmitted over open networks.

Data from central laboratories will be transferred electronically. In cases where data is transferred via non-secure electronic networks, data will be encrypted during transfer.

Some of the laboratory results (IGF-I SDS values) will be entered manually into the eCRF by Novo Nordisk personnel unrelated to trial conduct. The laboratory will provide all laboratory reports to the investigator for filing at trial site; however, the IGF-I SDS values and actual IGF values will not be available for the site staff until after the end of trial.

The subject and any biological material obtained from the subject will be identified by subject number and trial ID. Appropriate measures such as encryption or leaving out certain identifiers will be enforced to protect the identity of subjects in all presentations and publications as required by local, regional and national requirements.

16 Computerised systems

Novo Nordisk will capture and process clinical data using computerised systems that are described in Novo Nordisk Standard Operating Procedures and IT architecture documentation. The use and control of these systems are documented.

Investigators working on the trial may use their own electronic systems to capture source data.

17 Statistical considerations

If necessary, a statistical analysis plan (SAP) may be written in addition to the protocol, including a more technical and detailed elaboration of the statistical analyses. In case a SAP is written, it will be finalised before database lock.

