17.3 Primary endpoint

- Incidence of adverse events, including injection site reactions, from first administration of trial product to end of the trial period (53 weeks including follow-up)

The primary objective of the trial is to evaluate the safety of once weekly dosing of somapacitan during 52 weeks of treatment in Japanese GHD subjects previously treated with hGH and analysis of AEs will be the primary tool for achieving this. AEs will be analysed using descriptive statistics. All AEs with onset after the first administration of trial product and up until end of the trial (53 weeks) or 14 days after last trial drug administration, whichever comes first, will be included in the analysis. The AEs will be summarised by treatment, MedDRA (Medical Dictionary for Regulatory Activities) system organ class and MedDRA preferred term. The descriptive statistics will include the number and percentage of subjects who experienced AEs, the number of events and rate per 100 person years. AEs will be listed by treatment and subject with information on severity, relationship to trial product and demographics. AEs with onset before first dosing will be reported in a separate listing. AEs with onset 14 days or more after last trial drug administration will be reported in a separate listing.

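### Do the two fixed-dose IGF-I samples fall outside every safety analysis?

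*Combined protocol and SAP*

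**What the plan says.** Section 8.5.2 treats IGF-I and IGFBP-3 as safety laboratory measurements: "IGF-I and IGFBP-3 samples will be collected at screening and every second visit during the titration period and throughout the fixed-dose period". The only use it states for the results is dose adjustment during titration.

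On who sees the results:

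- Section 8.5: "The investigator must review all laboratory results for concomitant illnesses and AEs and report these". No exception is written there, and every laboratory report must be signed to show it was reviewed.
- Section 5.3.1: "IGF-I SDS results will not be made available to the investigator during the trial". The same sentence covers IGF-I and IGFBP-3.
- Section 15: "the IGF-I SDS values and actual IGF values will not be available for the site staff until after the end of trial". This is the second half of a sentence whose first half has the laboratory send all its reports to the investigator for filing.
- Section 8.5, on the sponsor's two-monthly review: "Surveillance of laboratory safety data (with the exception of PK, biomarkers and anti-drug antibody data) will be performed by a medical specialist".

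On what is analysed:

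- Section 17.3 says of the primary safety objective that "analysis of AEs will be the primary tool for achieving this".
- Section 12.1.1 defines a laboratory adverse event as "a clinical laboratory abnormality which is clinically significant, i.e. an abnormality that suggests a disease and/or organ toxicity", and adds that it must be severe enough to need active management.
- Section 17.4.1.2 takes change from baseline to week 52 in clinical laboratory results. Its list is introduced by the word *including* and names haematology, biochemistry, glucose, insulin, HOMA estimates and HbA1c, but not IGF-I. All secondary safety endpoints are to be analysed descriptively.

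**The concern.** Put together, these sections seem to leave the late IGF-I values with no reader and no table. During titration the eCRF algorithm acts on IGF-I, and a site can infer the SDS band from the dose step. After week 20 neither applies. The site cannot see the value, the sponsor's periodic review leaves biomarkers out, and adverse event collection for a subject closes at week 53 (section 12.2). End of trial is the last subject's last visit (section 7), so results are released only after a subject's reporting window has shut. An abnormal IGF-I value in the fixed-dose period therefore cannot, on its own, enter the adverse event tables in either arm.

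If section 17 also offers no summary, an absence of IGF-I findings would carry no information, yet a reader might take it as reassurance about 32 of the 52 treatment weeks (62%). Section 8.5 also appears to order a review that sections 5.3.1 and 15 make impossible.

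**Working it through.** **1. The samples.** The biomarker row of the flow chart marks visits 1, 3, 5, 7, 9, 11, 13 and 15: one at screening, five in titration, and two in the fixed-dose period (32W+4D and 51W+4D). With 60 subjects (60 × 3/4 = 45 and 60 × 1/4 = 15, as in section 17.1), that is up to 60 × 2 = 120 fixed-dose values: 90 on somapacitan and 30 on daily treatment.

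**2. The timing.** Week 20 is day 140, 32W+4D is day 32 × 7 + 4 = 228, and week 52 is day 364. The first sample after the last titration step comes 228 − 140 = 88 days later, and 364 − 228 = 136 days of the treatment period follow it.

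**3. Review against withholding.** Section 15 gives a general rule (all reports go to the site) and then, after *however*, an exception for IGF-I. Section 5.3.1 states the same exception and extends it to IGFBP-3. An investigator can meet section 8.5 by reviewing and signing every result received. What is missing is a pointer in 8.5 to the exception stated twice elsewhere.

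**4. The adverse event route.** Under section 12.1.1 an IGF-I SDS above +2 is not in itself an adverse event; it must also be judged clinically significant and need active management. Symptoms remain reportable at every contact. Glucose, insulin, HOMA estimates and HbA1c are measured at visits 13 and 15 and are not withheld. The withholding applies to both arms alike, so it does not tilt the comparison of adverse events.

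**5. The laboratory route.** The list in 17.4.1.2 is open, and section 8.5.2 files IGF-I among the safety laboratory assessments, so IGF-I fits the endpoint. Descriptive statistics are not restricted to means; ranges and counts by SDS band are equally allowed. Visit 13 falls outside a change to week 52 for every laboratory variable drawn then, including haematology, biochemistry and glucose, so that is no special gap for IGF-I.

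**6. Can the stakes be sized?** Section 5.5 gives a target range for the steady-state mean of −0.5 to +1.75, with midpoint (−0.5 + 1.75)/2 = 0.625. No SD is given. Assume a normal distribution and P(SDS > 2) = 1 − Φ((2 − m)/s):

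| Assumed mean m | s = 1.0 | s = 1.5 |
|---|---|---|
| 0 | 2.3%, 1.0 of 45 | 9.1%, 4.1 of 45 |
| 0.625 | 8.5%, 3.8 of 45 | 18.0%, 8.1 of 45 |
| 1.0 | 15.9%, 7.1 of 45 | 25.2%, 11.4 of 45 |

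The result runs from 1 to 11 subjects depending on what is assumed. It also ignores up to five titration steps that reduce the dose when SDS exceeds +2, and it takes the target midpoint to hold at the sampling time. It shows that a small mean change can coexist with high individual values, but not that this would happen here.

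**7. What a count could show.** The exact 95% upper limit for no events is 1 − 0.025^(1/n): 7.9% for 0 of 45 and 21.8% for 0 of 15. One daily-arm subject is 1/15 = 6.7 percentage points. Any such table describes and does not test.

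**The case for a change.** The best case for a change is that it is cheap and the data matter to the trial's purpose. The protocol cites the maintained IGF-I profile in the 26-week trial as support for weekly dosing (sections 3.1.4 and 5.5), and this trial is meant to substantiate those data at 52 weeks. Drug concentrations get their own line in 17.4.1.3; IGF-I gets none. A separate SAP is optional, and none is reproduced in the document, so nothing commits the sponsor in advance to an IGF-I table.

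Part of this stands. IGF-I is not named in sections 4.2 or 17, section 8.5 states no exception, and no reader is named for the two late values. Naming the variable would be tidier.

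Two supports are weaker than they look. The arm difference reported in section 5.2 concerned subjects below −2, at baseline and during titration. It says nothing about high values on a fixed dose, and the protocol already answers it with inclusion criterion 6 and an added titration visit. The charge that a change-from-baseline endpoint conceals extreme values holds only if the summary is confined to means, which 17.4.1.2 does not require.

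**Conclusion.** No change is needed. What remains is a missing cross-reference in section 8.5 and a descriptive table that is permitted but not named. Both are gaps that competent staff fill without guidance: sites review the reports they receive, and analysts summarise IGF-I by arm and visit along with the other safety laboratory data. Following the plan as written makes no adverse event table, laboratory summary or fat-tissue ANCOVA wrong, so the effect on the trial's results is nil. A caveat in 17.3 or a prescribed layout by SDS band would be an addition to the plan, not the correction of an error.

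This rests on three readings: that the word *including* in 17.4.1.2 leaves the list open, that IGF-I belongs to it because section 8.5.2 files it as a safety assessment, and that the withholding in sections 5.3.1 and 15 is deliberate. Who, if anyone, looks at the late values during the trial is for the sponsor to decide. The tail counts above rest on assumed means and SDs and should not be cited as a size.

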17.1 Sample size calculation

PMDA has requested 52 weeks safety data for a total of 60 Japanese GHD subjects previously treated with hGH, to further substantiate the data from the 26 weeks global safety trial NN8640-4043.

The sample size is not based on any formal calculations and does not account for withdrawals in the final sample size. 60 subjects should be randomised in a 3:1 ratio between somapacitan (45 subjects) and Norditropin[®] FlexPro[®] (15 subjects).

17.2 Definition of analysis sets

Two analysis sets are defined.

The full analysis set (FAS) used for evaluations of efficacy endpoints includes all randomised subjects that received at least one dose of randomised treatment. Only in exceptional cases may subjects be excluded from the FAS. Subjects will be analysed “as randomised”.

The safety analysis set (SAS) used for evaluations of safety endpoints includes all randomised subjects that received at least one dose of randomised treatment. Subjects will be analysed “as treated”.

The subjects or observations to be excluded, and the reasons for their exclusion must be documented and signed by those responsible before DBL. The subjects and observations excluded from analysis sets, and the reason for this, will be described in the CTR.

17.3 Primary endpoint

- Incidence of adverse events, including injection site reactions, from first administration of trial product to end of the trial period (53 weeks including follow-up)

The primary objective of the trial is to evaluate the safety of once weekly dosing of somapacitan during 52 weeks of treatment in Japanese GHD subjects previously treated with hGH and analysis of AEs will be the primary tool for achieving this. AEs will be analysed using descriptive statistics. All AEs with onset after the first administration of trial product and up until end of the trial (53 weeks) or 14 days after last trial drug administration, whichever comes first, will be included in the analysis. The AEs will be summarised by treatment, MedDRA (Medical Dictionary for Regulatory Activities) system organ class and MedDRA preferred term. The descriptive statistics will include the number and percentage of subjects who experienced AEs, the number of events and rate per 100 person years. AEs will be listed by treatment and subject with information on severity, relationship to trial product and demographics. AEs with onset before first dosing will be reported in a separate listing. AEs with onset 14 days or more after last trial drug administration will be reported in a separate listing.

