4.1 Objectives

Primary objective

- To evaluate the safety of once weekly dosing of somapacitan during 52 weeks of treatment in Japanese GHD subjects previously treated with hGH

Secondary objective

- To evaluate the efficacy of once weekly dosing of somapacitan by measuring the effect on abdominal adipose tissue during 52 weeks of treatment in Japanese GHD subjects previously treated with hGH
- To evaluate the degree of treatment satisfaction of once weekly dosing of somapacitan during 52 weeks of treatment in Japanese GHD subjects previously treated with daily hGH

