4.2 Endpoints

4.2.1 Primary endpoint

- Incidence of adverse events, including injection site reactions from first administration of trial product to end of the trial period (53 weeks including follow-up)

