6.4 Criteria for premature discontinuation of trial product

Efforts must be made so that subjects attend and complete all scheduled visit procedures. Subjects should stay in the trial irrespective of lack of adherence to randomised treatment, lack of adherence to visit schedule or missing assessments. Only subjects who decline any further contact with the site in relation to the trial will be considered as withdrawn from the trial (see section [6.5](#)).

The subject may be prematurely discontinued from trial product at the discretion of the investigator due to a safety concern or if judged non-compliant with trial procedures.

The subject must be prematurely discontinued from trial product if the following applies:

1. Included in the trial in violation of the inclusion and/or exclusion criteria
2. Pregnancy
3. Intention of becoming pregnant
4. Simultaneous participation in another clinical trial of an approved or non-approved investigational medicinal product.
5. AE: If a subject reports symptoms which are considered unacceptable by the subject or the investigator, regardless of relationship to trial product, treatment must be discontinued
6. If physicians definitely diagnose diabetes mellitus in accordance with diagnostic criteria established by the Japan Diabetes Society²¹ during the course of the trial the subject should be discontinued from treatment

See Section [8.1](#) for procedures to be performed for subjects discontinuing trial product prematurely.

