Re-sampling of screening parameters is ONLY allowed during an unscheduled visit (see section [8.8](#)) if samples are lost or damaged before arriving at the analysing laboratory, or if the analysis failed at the laboratory.

Premature discontinuation of trial product: If a subject prematurely discontinues trial product, the investigator must undertake procedures similar to those for week 51+4 days as soon as possible, however, the subject should be encouraged to follow all remaining site visits in the trial according to the trial flow chart. The follow-up visit (week 53) must be performed at least two weeks after last administration of somapacitan and at least 8 days after last administration of Norditropin[®] FlexPro[®].

The primary reason for premature discontinuation of trial product must be specified in the end-of-treatment form in the eCRF, and final drug accountability must be performed. A treatment discontinuation session must be made in the IWRS.

Withdrawal from trial: If a subject withdraws consent, the investigator must aim to undertake procedures similar to those for week 51+4 days as soon as possible. If the subject agrees, the follow up visit (week 53) must be performed at least two weeks after last administration of somapacitan and at least 8 days after last administration of Norditropin[®] FlexPro[®].

The end-of-treatment form and the end-of-trial form must be completed, and final drug accountability must be performed even if the subject is not able to come to the trial site. A treatment discontinuation session must be made in the IWRS, and in the eCRF it must be specified that the subject will not participate in subsequent visits in the trial. The case book must be signed.

Although a subject is not obliged to give his/her reason(s) for withdrawing consent, the investigator must make a reasonable effort to ascertain the reason(s), while fully respecting the subject's rights. Where the reasons are obtained, the primary reason for withdrawing consent must be specified in the end-of-trial form in the eCRF system.

Review of diaries, patient reported outcomes (PROs), laboratory reports etc. must be documented either on the documents or in the subject's medical record.

If clarification of entries or discrepancies in the diary or patient reported outcomes is needed, the subject must be questioned and a conclusion made in the subject's medical record. Care must be taken not to bias the subject.

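### The primary AE endpoint runs to week 53, but its only planned summary stops 14 days after last dose, and the handling of day 14 itself is unclear

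*Combined protocol and SAP*

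**What the plan says.** Section 4.2.1 gives the primary endpoint as "Incidence of adverse events, including injection site reactions from first administration of trial product to end of the trial period (53 weeks including follow-up"). Section 17.3 repeats it. Neither definition has a limit tied to the last dose.

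The analysis text in Section 17.3 does have one. AEs with onset after first dose and up to the end of the trial "or 14 days after last trial drug administration, whichever comes first, will be included in the analysis". It adds that "AEs with onset 14 days or more after last trial drug administration will be reported in a separate listing". The planned statistics are counts and percentages of affected subjects, event counts, and rates per 100 person-years. All are descriptive and shown by treatment.

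Subjects who stop trial drug are not meant to leave. Section 6.4: "Subjects should stay in the trial irrespective of lack of adherence to randomised treatment". Section 8.1: "the subject should be encouraged to follow all remaining site visits in the trial according to the trial flow chart". Section 12.2 has AEs collected "until the end of the post-treatment follow-up period (week 53"), with no reference to last dose.

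No other section plans an AE summary over the full window. Section 17.4.1.2 covers other safety endpoints, and Section 17 says only that a separate SAP may be written if needed.

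**The concern.** Section 17.3 makes AE analysis the main means of meeting the primary objective. A reader of the endpoint line would expect the primary table to hold every AE from first dose to week 53. For early stoppers who remain in follow-up it does not: the data are collected, but no planned count, percentage or rate uses them. The endpoint and its one summary are different quantities, and nothing labels the summary as on-treatment.

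A second, smaller matter is the boundary. The inclusion rule runs up to 14 days after last dose and the listing rule starts at 14 days. Whether day 14 belongs to the table, the listing or both depends on how the first rule is read. If the planned schedule puts that day on the final visit in one arm only, the ambiguity is not symmetric.

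**Working it through.** There is no planned figure to reproduce: Section 17.1 says the sample size has no formal calculation. The check is day arithmetic, with first dose on Day 0 (Section 5.3).

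**Inputs**
- End of trial: week 53 = 53 × 7 = day 371.
- Last planned somapacitan dose: before the visit at week 51 + 4 days (Section 5.3). Weekly dosing from Day 0 puts it on day 51 × 7 = 357. This is inferred; the protocol does not state the day.
- Last planned Norditropin dose: seven daily doses in week 51, three of them from the visit on day 361 onward (Section 5.3), so days 357 to 363 and a last dose on day 363.
- Allocation: 45 somapacitan, 15 Norditropin (Section 17.1).

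**Check on the inferred days.** Week 53 falls 371 − 357 = 14 days after the last somapacitan dose and 371 − 363 = 8 days after the last Norditropin dose. Section 8.1 says that after early stopping the follow-up visit "must be performed at least two weeks after last administration of somapacitan and at least 8 days after last administration" of Norditropin. Both gaps agree.

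**Where the windows part.** With last dose on day L, and day 14 counted as included, the summary ends on day min(371, L + 14). It falls short of the endpoint window when L + 14 < 371, that is L < 357. Uncounted days for a subject followed to week 53 = 357 − L.

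| Last dose | L | Summary ends | Uncounted days | Share of 371 |
|---|---|---|---|---|
| First dose only | 0 | 14 | 357 | 96.2% |
| Week 20 | 140 | 154 | 217 | 58.5% |
| Week 32 | 224 | 238 | 133 | 35.8% |
| Week 42 | 294 | 308 | 63 | 17.0% |
| Week 50 | 350 | 364 | 7 | 1.9% |
| Week 51 | 357 | 371 | 0 | 0% |

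A somapacitan subject who misses only the final weekly dose is the week-50 row. A Norditropin subject who misses the last six daily doses still has L = 357 and 0 days uncounted. Missing all seven gives L = 356 and 1 day (0.3%).

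**Scale across the trial.** No discontinuation rate is given. The under-7% figure in Section 17.4.1.1 concerns missing CT data only. As an assumed range, if 2% to 15% of subjects stopped at week 20 and everyone was followed to week 53, the uncounted share of follow-up would be 0.02 × 217/371 = 1.2% to 0.15 × 217/371 = 8.8%.

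**Effect on a percentage.** One affected subject changes a row by at most 1/45 = 2.2 points (somapacitan) or 1/15 = 6.7 points (Norditropin). That bound is reached only if all of the subject's events in that row fall in the uncounted days.

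**The boundary, for on-schedule completers with follow-up on day 371**
- Day 14 read as included: a somapacitan onset on day 371 is analysed and also sent to the late listing.
- Day 14 read as excluded: that onset goes only to the listing, so one day is uncounted in the somapacitan arm.
- Norditropin: 363 + 14 = 377, after day 371. An onset at the week-53 visit is on day 8 after last dose and is analysed on either reading.

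**The case against.** The strongest reply is that Section 17.3 simply makes the endpoint operational. The rule is explicit and fixed in advance, and it sits in the same section as the endpoint line. A window tied to exposure fits the objective, "To evaluate the safety of once weekly dosing of somapacitan during 52 weeks of treatment in Japanese GHD subjects previously treated with hGH". It also fits a safety set analysed by treatment received (Section 17.2) and the switch of early stoppers to a marketed product (Section 5.4). Fourteen days equals the minimum somapacitan follow-up interval in Section 8.1. A full-window table would place events on another product under the trial arm. All of this stands as a defence of the window. It does not make the summary equal to the endpoint as worded.

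The affected group may also be small. Remaining visits are only encouraged, and a subject who ends participation at the minimum follow-up interval has little or nothing uncounted. That stands too, and the documents do not allow the number to be estimated.

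On the boundary, the two rules can be read as a clean partition, with day 14 going to the listing alone. So a double classification is not established. The partition reading, however, drops the week-53 visit day from the somapacitan summary while keeping it for Norditropin, so it does not remove the problem.

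A reader might infer more than this:
- That late AEs are lost. They are collected to week 53 and listed.
- That early stoppers' AEs are not summarised at all. They are, up to the cut-off.
- That the 14-day rule biases the comparison of arms. The asymmetry shown for on-schedule completers is one onset day in a descriptive table.

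**Conclusion.** The mismatch is real and minor. The primary endpoint is AE incidence to week 53, while its only planned summary covers first dose to the earlier of week 53 and 14 days after last dose. The two differ only for subjects whose last dose is before about day 357 and who stay in follow-up. For such a subject the gap ranges from a day or so to nearly the whole trial. The number of such subjects is unknown.

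The day-14 boundary needs one stated rule whichever reading was meant. That its effect falls on the somapacitan arm alone rests on three conditions: dosing on schedule, a last somapacitan dose on day 357, and follow-up on day 371. The visit-window row of the flow chart is not legible enough in the text available to say whether the week-53 visit may fall later. The figure of 0 uncounted days for on-schedule somapacitan completers also depends on including day 14; otherwise it is 1 day.

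**What to change.** In Section 17.3:

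1. Keep the 14-day summary and label it as the on-treatment window.
2. Add one descriptive table of all AEs from first dose to week 53, regardless of discontinuation, labelled as including events after a switch to other treatment. This is the endpoint as Section 4.2.1 states it. At minimum, restate the endpoint in Sections 4.2.1 and 17.3 with the 14-day limit so that endpoint and summary match.
3. State that onsets up to and including day 14 are analysed, and restrict the listing to onsets more than 14 days after last dose. On-schedule completers in both arms then have the week-53 visit day treated alike.

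As a clarification, say that each rate takes its person-years from the same window as its events.

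The cost is a few lines of text and one table from data already collected. The drawback is that the added table puts some events on other treatment under the trial arm, so it needs the label.
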